## 1.0 Background

Nesina tablets (hereinafter, Nesina) are dipeptidyl peptidase-4inhibitors (hereinafter, DPP-4inhibitors) and oral hypoglycemic drugs mainly characterized by glucose level-dependent insulin secretion promotion via a GLP-1 increase and pancreas protection. Since oral hypoglycemic drugs have been generally used for a long period in patients and since multiple hypoglycemic drugs may be used simultaneously, it is important that long-term results of oral hypoglycemic drugs should be obtained from a daily clinical practice. The Specified Drug-use Survey of Nesina has been conducted in type 2 diabetes mellitus patients who have had an inadequate response to diet/exercise therapies only or diet/exercise therapies plus  $\alpha$ -glucosidase inhibitors, thiazolidines, sulfonylureas, or biguanides. In the future, the specified drug-use survey of complication with Nesina and insulin preparations and insulin secretagogues is also expected to be conducted.

Therefore, the Nesina Tablets Specified Drug-use Survey "Type 2 Diabetic Patients Receiving Combination Therapy With a Hypoglycemic Agent (e.g., Insulin Preparations or Rapid-acting Insulin Secretagogues)" (hereinafter, this survey) is planned aiming to evaluate the safety and efficacy of Nesina when administered for 1 year in type 2 diabetic patients who have had an inadequate response to hypoglycemic agents (e.g., insulin preparations, rapid-acting insulin secretagogues) in addition to dietary/exercise therapy in daily medical practice.

This survey is conducted according to the relevant regulatory requirements including the GPSP ordinance.

## 2.0 Objectives

This survey is designed to evaluate the safety and efficacy of long-term use of alogliptin tablets (Nesina Tablets) in type 2 diabetic patients who have had an inadequate response to hypoglycemic agents (e.g., insulin preparations or rapid-acting insulin secretagogues)\* in addition to dietary/exercise therapy in daily medical practice.

\*Hypoglycemic agents which have not been used in the past Nesina Specified Drug-use Survey (i.e., other than  $\alpha$ -glucosidase inhibitors, thiazolidines, sulfonylureas, and biguanides)

## 3.0 Number of Planned Participants and the Rationales

### 3.1 Number of Planned Participants

1,000 participants

### 3.2 Rationales

The Specified Drug-use Survey of Nesina has been conducted in type 2 diabetes mellitus patients who have had an inadequate response to diet/exercise therapies only or diet/exercise therapies plus  $\alpha$ -glucosidase inhibitors, thiazolidines, sulfonylureas, or biguanides. In the future, the specified drug-use survey of complication with Nesina and insulin preparations and insulin

secretagogues is also expected to be conducted.

Therefore, the planned participants was established as 1,000 to collect as many as participants who receive a long-term complication therapy with Nesina and these hypoglycemic agents (e.g., insulin preparations, rapid-acting insulin secretagogues).

In the pooled tabulation of participants in the past Nesina Specified Drug-use Survey (as of November 30, 2013; Safety Analysis Set, 10,025 participants), the proportion of participants was as follows: elderly, 58.0%; renal impairment participants, 15.1%; and hepatic impairment participants, 13.3%. By establishment of the planned participants of 1,000 in this survey, data will be collected from approximately 600 elderly participants, approximately 150 renal impairment participants, and approximately 100 hepatic impairment participants. This establishment is not based on the statistical evidence.

#### 4.0 Patients for Survey

Patients with type 2 diabetes mellitus. However, participants must meet the inclusion criteria and none of the exclusion criteria, described below. Refer to the Precaution in the package insert.

##### 4.1 Inclusion Criteria

Patients who meet the following criterion are included in this survey:

Patients who have had an inadequate response to the following medications/therapies:

- Use of one hypoglycemic agent such as insulin preparations and rapid-acting insulin secretagogues, excluding other types of hypoglycemic agents (e.g.,  $\alpha$ -glucosidase inhibitors, thiazolidines, sulfonylureas, biguanides)\*, in addition to dietary/exercise therapy

\*For use of Nesina Tablets in combination with these agents, a specified drug-use survey is currently ongoing.

##### 4.2 Exclusion Criteria

Patients who meet any of the following criteria are excluded from this survey:

Patients with contraindications for Nesina Tablets

- (1) Those with severe ketosis, in a state of diabetic coma or precoma, or with type 1 diabetes mellitus [Quickly rectifying hyperglycemia with administration of intravenous fluid or insulin is essential in these patients; therefore, administration of Nesina Tablets is not appropriate.]
- (2) Those with severe infections, before or after surgery, or with serious trauma [Controlling blood glucose with an injection of insulin is desirable for these patients; therefore, administration of Nesina Tablets is not appropriate.]
- (3) Those with a history of hypersensitivity to any of the ingredients of Nesina Tablets

#### 5.0 Dosage and Administration

For adults, 25 mg of alogliptin is usually administered orally once daily. Refer to the Precaution

in the package insert. For renal impairment patients, refer to the Precaution with Respect to Dosage and Administration in the package insert.

## 6.0 Number of Scheduled Sites by Department

Internal medicine or other department: Approximately 200 sites

## 7.0 Methods

### 7.1 Observation period

12 months

### 7.2 Request for Sites and Agreement

The survey is conducted using the paper survey sheet. Before asking survey, the parson in charge of medical information in Takeda Pharmaceutical Company Limited. (Hereinafter, Takeda MRs) will fully explain to the Investigator about the objectives, details, and methods of this survey, based on “Request for Cooperation of Specified Drug-use Survey,” “Summary for Survey,” “Patient Enrollment Sheet (sample),” and “Survey Sheet (sample)” and will finalize written agreement with survey sites to ask requests for surveillance within the specified period.

### 7.3 Patient Enrollment Methods patients

This survey is conducted by Fax using Central Enrollment System. The Investigator will enroll patients for whom Nesina was prescribed after the start date of agreement with a survey site, by faxing to the Central Enrollment Center (refer to Section 12.2) the “Patient Enrollment Sheet” including the information regarding patient enrollment (refer to Section 9.1) before 14 days after the Nesina prescription date (define the prescription date as “0 day” and one day after the prescription date as “1 day”). Patients for whom Nesina prescription is scheduled cannot be enrolled earlier. The participant who assessed as ineligible for the survey for any reason cannot be enrolled in the survey. The Investigator will enroll a new participant using the “Patient Enrollment Sheet” supplied by the Takeda MR. The Takeda MR will supply for the Investigator the survey sheet issued after the Central Enrollment Center enrolled the participant.

### 7.4 Creation and Submission of Survey Sheet

The Investigator will create the survey sheet for all enrolled participants and submit it to the Takeda around within 1 month after the end of the observation period. If Nesina administration cannot be confirmed, specify it (do not specify other columns).

For participants who early discontinue treatment with Nesina during the observation period for any reason, the Investigator will create the survey sheet for him/her and submit it to the Takeda around within 1 month after the end of necessary observation. However, for participants who early discontinue treatment with Nesina due to an adverse event, the Investigator will continue

observation even after treatment discontinuation, wherever possible, until the adverse event resolve or is resolving and will create the survey sheet and submit it to the Takeda.

### 7.5 Measures for Development of Serious Adverse Events

In case of development of a serious adverse event in the observation period, the Investigator will immediately contact the parson in charge in Takeda Pharmaceutical Company Limited. (person in charge in Takeda). If the person in charge in Takeda requests additional detailed information, the Investigator will provide it.

### 8.0 Scheduled Period

Survey period: June 2014 to June 30, 2017

Patient enrollment period: June 2014 to June 30, 2016\*

\*Even if Nesina is prescribed before June 30 2016, the patients cannot be enrolled (fax of the Patient Enrollment Sheet) after July 1 2016.

In case that the enrolled participants reach the scheduled number of participants in the survey before June 30 2016, the enrollment will close earlier than the scheduled patient enrollment period. If patient enrollment period is shorten, the survey period will be also changed according to the shorten period.

### 9.0 Matters to be Surveyed

The Investigator will describe the data described below in the Patient Enrollment Sheet and the survey sheet. The schedule of this survey is shown in the Appendix.

#### 9.1 Description Details in Patient Enrollment Sheet

##### 1) Matters to be surveyed

Name of survey site, name of the investigator who describe in the Patient Enrollment Sheet, Nesina prescription date, Patient ID Number, patient initial, sex, birth date, inclusion criteria assessment, and exclusion criteria assessment

##### 2) Survey period

At patient enrollment

#### 9.2 Description Items in Survey Sheet

##### 9.2.1 Front Cover of Survey Sheet

Last description date in the survey sheet and name of the Investigator who described the survey sheet

##### 9.2.2 Patient Demographics

###### 1) Matters to be surveyed

Diagnosis period of type 2 diabetes mellitus, category of clinical practice, disposition of hypersensitivity (yes/no and detail), concurrent disease (yes/no and detail), past medical

history (yes/no and detail), height, smoking history, drinking history, presence or absence of serum creatinine within 1 month after the start of Nesina treatment, serum creatinine level (if serum creatinine present), and severity of renal impairment and rationale for the assessment (if serum creatinine absent).

2) Survey period

At the start of Nesina treatment

9.2.3 Details of Treatment

1) Matters to be surveyed

Details of Nesina treatment (daily dose, administration period, and reason for discontinuation), and status of concomitant medications (hypoglycemic agents\*) (yes/no, drug name, daily dose, route of administration, administration period, and objective of administration)

\*Hypoglycemic agents which are discontinued within 3 months prior to Nesina treatment are included.

2) Survey period

Period from the start of Nesina treatment to 12 months after treatment (or treatment discontinuation)

9.2.4 Compliance with Nesina and Compliance with Diet/Exercise Therapy

1) Matters to be surveyed

Compliance with Nesina\* and compliance with diet/exercise therapy\*\*

\*Criteria for assessment of compliance with Nesina

1.  $\geq 90\%$  (A participant won't miss administration, or even if he/she missed administration, the frequency is twice or three times a month.)
2.  $\geq 70\%$  (A participant missed administration once or twice weekly.)
3.  $\geq 50\%$  (A participant missed administration three times a week.)
4.  $< 50\%$  (A participant missed administration four times or more a week.)

\*\*Criteria for assessment of compliance with diet/exercise therapy

1.  $\geq 90\%$  (A participant complied as instructed.)
2.  $\geq 70\%$  (A participant mostly complied as instructed.)
3.  $\geq 50\%$  (A participant did not complied well as instructed.)
4.  $< 50\%$  (A participant did not mostly complied as instructed.)
5. Not performed
6. Unknown

## 2) Survey period

At the start of Nesina treatment (compliance with diet/exercise therapy only), 1 month, 3 months, 6 months, and 12 months after the start of treatment (or treatment discontinuation)

### 9.2.5 Laboratory/Observation Parameters

#### 9.2.5.1 Vital Signs

##### 1) Laboratory/observation parameters

Pulse rate, blood pressure (systolic/diastolic), and weight

##### 2) Survey period

Each time point at the start of Nesina treatment, 1 month, 3 months, 6 months, and 12 months after the start of treatment (or treatment discontinuation)

#### 9.2.5.2 Laboratory Values

##### 1) Laboratory parameters

HbA1c (NGSP value, same hereafter), fasting glucose, fasting insulin, fasting glucagon, fasting triglyceride, total cholesterol, HDL-cholesterol, LDL-cholesterol, serum creatinine, BUN, urinary albumin (corrected by creatinine), AST, ALT,  $\gamma$ -GTP, ALP, total bilirubin, amylase, and lipase

##### 2) Survey period

Each time point at the start of Nesina treatment, 1 month, 3 months, 6 months, and 12 months after the start of treatment (or treatment discontinuation)

#### 9.2.5.3 Electrocardiography

##### 1) Observation Parameters

Electrocardiograms (assessment and findings)

##### 2) Survey period

Each time point from the start of Nesina treatment to 12 months after treatment (or treatment discontinuation)

#### 9.2.5.4 Tests for Waist Circumference, Coronary Arteriosclerosis, and Arteriosclerosis

##### 1) Observation Parameters

Tests for waist circumference,\* coronary arteriosclerosis and arteriosclerosis\*\* (e.g., pulse wave velocity, cardio-ankle vascular index, intima-media thickness, intra-vascular ultrasound)

\*Measure the waist diameter during light expiration at standing position and at the level of the navel. If the lower deviation of the navel occurs because of significant abdominal fat accumulation, measure the waist diameter at the level of the midpoint between the inferior rib border and anterior superior iliac spine.

\*\*Any methods can be used. In principle, however, use the same methods for each test. If there are no

devices for measurement, the tests can be omitted.

## 2) Survey period

Each time point from the start of Nesina treatment to 12 months after treatment (or treatment discontinuation)

### 9.2.5.5 Other Parameters

#### 1) Observation parameters

Pregnancy during the observation period (yes or no) (females only)

In case of pregnancy in the observation period, the Investigator will immediately contact the person in charge in Takeda. The Investigator will provide detailed information (including the information until the delivery, as possible, such as preterm delivery) using the separate pregnancy sheet after the request from the person in charge in Takeda.

#### 2) Survey period

Period from the start of Nesina treatment to 12 months after treatment (or treatment discontinuation)

### 9.2.6 Adverse Event

#### 1) Matters to be surveyed

Presence or absence of adverse events (refer to Table 1), term of adverse events, onset date, seriousness and the reason (refer to Table 2), presence or absence of Nesina discontinuation, outcome assessment date, outcome, and causal relationship to Nesina\* (refer to Table 3).

If the outcome is assessed as Not resolved or Unknown and if the causal relationship cannot be assessed, the participant will be followed up, wherever possible.

The detailed information (e.g., clinical course, laboratory tests for diagnosis) will be collected as possible for development of hypoglycemia, acute pancreatitis, renal impairment / jaundice, skin disorder including oculomucocutaneous syndrome (Stevens-Johnson syndrome) and erythema multiforme, rhabdomyolysis, intestinal obstruction, interstitial pneumonia, angioedema, infection, malignant tumor, pemphigoid, and cardiovascular system-related event (e.g., symptomatic coronary artery disease, cerebrovascular disorder, arteriosclerosis obliterans, cardiovascular death, sudden death)

\*If the causal relationship to Nesina is assessed as Not related, collect the rationales for assessment. If the relationship is assessed as Not assessable, collected the reason for Not assessable.

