#### 2) Survey period

Period from the start of Nesina treatment to 12 months after treatment (or treatment discontinuation)

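### Read literally, Protocol 9.2.6 gives no outcome follow-up to an open adverse event whose causality has been assessed, and the end of adverse event collection for patients who discontinue is not reconciled across sections

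*Protocol*

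**What the plan says.** **Follow-up.** The trigger in Protocol 9.2.6 joins an outcome condition and a causality condition: "If the outcome is assessed as Not resolved or Unknown and if the causal relationship cannot be assessed, the participant will be followed up". The duty is qualified as applying where it can be done. Table 3 of the protocol has three causality classes (Related, Not related, Not assessable) and reserves the last for missing information. The next paragraph of 9.2.6 asks for details such as clinical course, as far as possible, for a list of named risks that includes acute pancreatitis, malignant tumor and pemphigoid. It attaches no causality condition. For a patient who stops Nesina because of an adverse event, Protocol 7.4 continues "observation even after treatment discontinuation, wherever possible, until the adverse event resolve or is resolving".

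**Collection period.** The survey period for adverse events in 9.2.6 is "Period from the start of Nesina treatment to 12 months after treatment (or treatment discontinuation", and the Appendix schedule has a discontinuation column. Protocol 7.1 gives the observation period as 12 months and does not mention discontinuers. Section 7.4 begins "For participants who early discontinue treatment with Nesina during the observation period for any reason" and asks for the sheet "around within 1 month after the end of necessary observation", without defining that end. Section 7.5 reads "In case of development of a serious adverse event in the observation period, the Investigator will immediately contact" the sponsor. Section 10.4.1 tabulates adverse events reported in the same observation period.

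**SAP.** Section 5.3 tabulates adverse drug reactions by outcome, and *Not resolved* and *Unknown* are reportable categories. Section 1.1 computes percentages over the whole Safety Analysis Set. Section 1.5 cuts laboratory and measured values relative to the last administration. No such cut-off or label is given for adverse events.

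**The concern.** An event judged related to Nesina and not yet resolved is one whose outcome a long-term safety survey most wants to know. Taken at its word, the 9.2.6 sentence creates no duty to find it out. About 200 sites complete paper sheets, and one sentence that can be read two ways invites two practices. An event not followed keeps its interim outcome, so the SAP 5.3 table would mix true non-resolution with events nobody went back to.

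The second part concerns what is counted. If one site stops recording at discontinuation and another records new events after it, the reported percentages combine two collection rules over one denominator, and nothing in the SAP output would show it.

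**Working it through.** The plan states no figure on this point, so the check sets the passages side by side and then illustrates size on assumed inputs.

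**1. What each rule reaches.** There are two open outcomes and three causality classes, so six combinations.

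| Open outcome | Related | Not related | Not assessable |
|---|---|---|---|
| Not resolved | 7.4 only, if the event caused discontinuation | same | 9.2.6 |
| Unknown | 7.4 only, if the event caused discontinuation | same | 9.2.6 |

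The literal *and* reaches 2 of 6. In the other four, an event in a patient who stays on treatment or stops for another reason meets neither rule.

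With *or*, all 6 are reached, together with *Not assessable* events having one of the other four outcomes in SAP 5.3. Across the full grid of 6 outcomes × 3 classes = 18, that is 6 + 4 = 10 combinations instead of 2.

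**2. When it matters.** A patient who stays on Nesina has scheduled time points at 1, 3, 6 and 12 months. The outcome and its assessment date go on a sheet submitted about a month after the period ends. For such patients the gap concerns events still open at sheet completion.

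**3. Which open events reach SAP 5.3.** That table covers adverse drug reactions, not all adverse events. SAP 1.1 as printed defines these as events judged *Not related*. The usual meaning would be the events not so judged. The definition needs its own correction, but on either meaning the table contains a class (*Not related* as printed, *Related* in the usual meaning) that the literal trigger does not reach.

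**4. Where the adverse event period ends for a discontinuer.**

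| Section | Stated end |
|---|---|
| 7.1 | 12 months; silent on discontinuers |
| 7.4 | Stopping is placed within the observation period; the end of necessary observation is undefined |
| 7.5, 10.4.1 | The observation period; no cut-off at discontinuation |
| 9.2.6 | Discontinuation, if before 12 months |

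No section says whether a new event after discontinuation is recorded.

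**5. Illustrations.** Planned N = 1,000 is from Protocol 3.1. All rates below are assumptions.

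- *Follow-up reached by 9.2.6* = share of events open × share of those not assessable. 20% × 5% = 1%; 20% × 20% = 4%. That leaves 19% or 16% of events open and outside 9.2.6, before 7.4 restores those that caused discontinuation.
- *Patient-time after discontinuation.* With a share d stopping evenly over 12 months, each loses 6 months on average, so the share is d × 6/12. For d = 10%: 600 of 12,000 patient-months = 5%. For d = 30%: 1,800 of 12,000 = 15%.
- *Effect on a crude percentage if collection stops at discontinuation.* Take a true 12-month risk of 5% and a constant hazard h = −ln(0.95) = 0.051293. The captured risk in discontinuers is 1 − 0.05/0.051293 = 2.52%. For d = 20%: 0.8 × 5% + 0.2 × 2.52% = 4.50%, so about 5 of 1,000 patients with a first event are missed. For d = 10% and 30% the crude figures are 4.75% and 4.26%, with 2.5 and 7.4 patients missed. These are upper bounds on the assumptions, because serious events after discontinuation may still arrive under 7.5.

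**The case against.** The best defence of the follow-up sentence is that it repeats *if*, so it can be read as two separate triggers, and that it does not exclude other follow-up. The named-risk paragraph gives a further route to clinical course for the events of most interest. Patients who stay on treatment remain under observation to 12 months, and 7.4 covers events that caused discontinuation whatever the causality. All of this stands, and it narrows the gap to open events outside 7.4 at sheet completion. It does not close it. An ambiguous duty is still ambiguous, and a request for details as far as possible is not a duty to establish the outcome.

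On the period, the discontinuation clause recurs throughout 9.2, and 7.4 can be read as a base rule with an exception for events that caused stopping. The survey evaluates Nesina when given for one year, so collection centred on treatment is a defensible design. That also stands. A reader might infer that 9.2.6 contradicts 7.1 and 7.5. The documents do not support this: there is a contradiction only if the observation period runs on after discontinuation. The wording of 7.4 hints that it does, but no section says so. The term is undefined, and no conflict is proven.

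**Conclusion.** The point holds as a gap in wording. On the literal reading, four of six open-outcome combinations have no stated follow-up outside 7.4, and the named-risk paragraph covers this only in part. The adverse event period for discontinuers is left unreconciled between 9.2.6 and sections 7.4, 7.5 and 10.4.1.

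A reader might go further and conclude that outcomes and late events are lost. That is a possibility, not a result. Section 7.4 keeps outcomes for events that caused stopping. A serious event after discontinuation may be reported under 7.5 and, if the observation period is still running, tabulated under 10.4.1. The exposure on the period side is therefore chiefly new non-serious events after discontinuation.

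No loss rate can be derived. The 1–4% and 5–15% figures rest on assumed shares of open events (20%), of *Not assessable* causality among them (5–20%) and of discontinuation (10–30%, evenly spread).

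**What to change.** - **Protocol 9.2.6, follow-up:** join the outcome condition and the causality condition with *or* in place of *and*. This changes one word. The cost is somewhat more outcome queries, including causality queries on events that have already resolved.
- **Protocol 7.1, 7.4, 7.5, 9.2.6 and 10.4.1:** reconcile these so that they state one end of the adverse event period for a patient who discontinues. Extending collection to 12 months for everyone is a design preference and is not required by this point.
- **SAP:** label each reported adverse event as on-treatment or after last dose. Onset date is collected under 9.2.6 and the last date of Nesina treatment is defined in SAP 1.1, so no new data item is needed. Events whose onset date was imputed should be flagged. The cost is one derived variable and a split of the existing tables.
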